**6. Number of Participants - Indicate the total number of anticipated participants to be recruited and enrolled.**

*Thirty subjects without a history of major knee injury/surgery and 30 subjects with a history of ACLR will be recruited for this study.*

**7. Recruitment Method - Describe who will be doing the recruitment of participants. Describe when, where, and how potential participants will be identified and recruited. Describe and attach materials that will be used to recruit participants (attach documents or recruitment script with the application).**

*The following recruitment methods will be used for this study.*

- a. *Two flyers have been created for recruitment (see attached, one flyer for uninjured participants and one for participants after ACLR). These flyers will be posted on bulletin boards at Arcadia University, posted on social media, emailed to students, and emailed to local physical therapists.*
- b. *Individuals with a history of ACL reconstruction will be recruited from local physical therapy clinics. Physical therapists will be notified of the study via email and/or phone and asked to have interested participants complete the "consent to contact form". Email/phone scripts are below. Good Sheppard/PENN Partners (GSPP) has a physical therapy clinic on campus. GSPP requires that a specific consent to contact form. Therefore, two consent to contact forms will be attached to this protocol. The physical therapists will only be informing the patients or patients guardians (if under 18 years old) that they may be eligible for a study being conducted at Arcadia University and having the patients/guardians complete the consent to contact form. Patients who complete the consent to contact form will be contacted by the PI who will determine eligibility and explain the study in more detail. Only the PI will be gaining consent with each subject.*

***Email script***

Dear \_\_\_\_\_,

*My name is [name]. I am a physical therapist and faculty member in the Physical Therapy Department at Arcadia University. I am running a study to test quadriceps strength and function after ACL reconstruction. For this study, I need to recruit participants without a history of major knee injury and participants with a history of ACL reconstruction. Please have any interested participants complete the “consent to contact form” attached to this email.*

*Sincerely,*

*[name]*

***Phone script***

*Hello. My name is [name]. I am a physical therapist and faculty member in the Physical Therapy Department at Arcadia University. I am running a study to test quadriceps strength and function after ACL reconstruction. For this study, I need to recruit participants without a history of major knee injury and participants with a history of ACL reconstruction. Can you provide me with your email so I can send you additional information regarding the study?*

**8. Procedures Involved - Describe procedures including:**

**Procedures**

*This study will consist of two collections separated by at least 48 hours. Each testing session will take approximately 2.5 hours to complete. All testing procedures will be administered pre and post a session of transcranial direct current stimulation (tDCS). The primary investigator ([name]) will collect all data. Doctoral students will assist data collection. The PI retains the right to stop testing if he determines that any aspect of the protocol puts the participant at more than minimal risk.*

*Individuals <18 years old will only complete strength testing and questionnaires at one testing session.*

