*Hypothesis 2.1: Patients after ACLR will demonstrate increased CSE (lower AMTs and steeper SLOPEs) after one session of active tDCS and no changes in CSE after placebo tDCS.*

*Hypothesis 2.2: Patients after ACLR will demonstrate greater RTD/isometric strength after one session of active tDCS and no changes in RTD/isometric strength after placebo tDCS.*

**Aim 2:** Determine the relationship between two measures of CSE and two measures of quadriceps muscle performance in patients after ACLR.

*Hypothesis 1.1: Greater CSE will be associated with greater quadriceps isometric strength and greater RTD.*

*Hypothesis 1.2: The correlation between CSE and RTD will be greater than the correlation between CSE and isometric strength.*

*Current outcomes following ACLR are less than optimal with patients demonstrating chronic quadriceps dysfunction related to altered movement patterns and the development of post-traumatic knee OA. Emerging evidence suggests that quadriceps dysfunction after ACLR is related to alterations in CSE. Therefore, interventions targeting CSE have the*

*potential to mitigate chronic quadriceps dysfunction, improve movement patterns, and improve outcomes. The proposed study is a logical and essential first step in determining the effect of tDCS, an intervention known to induce changes in excitability, on CSE and quadriceps performance in patients after ACLR. Upon completion of this study, I will have obtained the pilot data needed to apply for a larger grant to investigate the effects of multiple sessions of tDCS on CSE and quadriceps muscle performance, generating the evidence needed to introduce this intervention into the clinical practice.*

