**Transcranial direct current stimulation (tDCS)**

a-tDCS (Soterix 1x1, Soterix Medical Inc, NY, NY) will be delivered over the primary motor cortex contralateral to the surgical limb (i.e. hot spot for the vastus medialis muscle representation found during TMS testing). A pair of carbon electrodes placed in saline-soaked sponges (surface area: 5 x 7  $\text{cm}^2$ ) will be secured to the scalp using straps (Soterix EASYstrap). The anode will be centered over the hotspot while the cathode will be placed on the right supraorbital area. a-tDCS will be administered while the participant rides a stationary bike for 20 minutes. The bike seat will be adjusted for each participant so that maximal knee flexion range of motion will be 90 degrees. Participants will also be instructed to maintain a neutral ankle angle. Verbal feedback provided by an investigator will be provided throughout the intervention to maintain the neutral ankle position. The standardized seat position and ankle position is to prevent the participant from using their ankle plantarflexors during the pedaling motion. Stationary bike riding was chosen as this task is commonly performed early after ACLR with minimal stress to the healing graft and requires quadriceps activity. The first 5 minutes will serve as a warmup with the patient maintaining a rate of perceived exertion (RPE) of light or 1 out of 10. Over the next 10 minutes, the resistance will be increased to maintain a RPE of moderate or 3/10. The last 5 minutes will serve as a cool down at the same intensity/resistance as the warm up. Active a-tDCS will be applied at an intensity of 2mA with a 30-second ramp-up and 30-second ramp-down for the entire duration of bike riding, while the sham a-tDCS will be applied for only the first 30 seconds.

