**Data Analysis**

Independent t-tests will be used to examine demographic differences between the two groups. A 2 (limb) x 2 (group) ANOVA will be used to evaluate differences in strength, TMS, and fNIRS measures. Regression analyses will be used to determine the relationship between the CNS measures and quadriceps strength, and the relationship between the TMS and fNIRS measures.

**9. Compensation or Credit - Describe the amount and timing of any compensation or credit to participants. Identify the source of the funds to compensate participants**

*Each participant (≥18 years of age) will be paid \$100 for their participation in this study. Participants must complete both sessions to receive the compensation.*

*Each participant (<18 years of age) will receive \$50 for their participation in this study as they will only complete one session.*

**10. Risk to Participants - List the reasonably foreseeable risks, discomforts, or inconveniences related to participation in the research. Consider physical, psychological, social, legal, and economic risks.**

*Risks associated with Testing Procedures (TMS, strength testing)*

*There are no known long term risks of TMS. There is a very small risk of seizure, syncope, and change in auditory thresholds. A recent study examining adverse events of TMS concluded: "Our data suggest that single/paired-pulse and repetitive TMS, conducted within the published guidelines pose a very small increment over the background risks of everyday life to subjects without known risk factors." Screening potential participants for a prior history of seizures, syncope, and hearing impairments will allow us to exclude individuals at increased risk. Participants will be offered ear plugs if the sound from the TMS pulse is uncomfortable.*

*In the very unlikely event of a seizure, the following steps will be taken: 1) The participant will be positioned in the safest position to maintain an open airway (i.e. laying supine or side lying), 2) emergency personal will be contacted by dialing 911 (research assistant), 3) any objects will be moved away from the participant to prevent additional injury, 4) monitor vitals until emergency personal arrive.*

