*Most subjects report no discomfort from TMS although some do report mild discomfort over the site of stimulation. Some subjects report a mild headache following the procedure. This typically resolves within 24 hours and can be treated with over the counter analgesics (i.e. Tylenol, ibuprofen). If subjects do experience discomfort over the stimulation site, the intensity of the stimulator can be reduced to minimize this. The session will be terminated immediately if the subject reports discomfort that is beyond their tolerance. Subjects may experience mild muscle soreness 24-48 hours after the testing session. This is a normal physiologic response to strength testing and strength training. There are no risks or discomfort associated with strength testing. Strength testing is performed at regular intervals after ACL reconstruction.*

*Risks associated with transcranial direct current stimulation (tDCS)*

*tDCS have been used in a growing number of laboratories worldwide since 1985. In the present protocol, only a non-significant risk protocol is being employed by using tDCS. tDCS is very safe and there have been very few incidences of adverse events with tDCS. A recent meta-analysis of adverse effects associated with tDCS reviewed 209 experiments (3836 subjects). The main adverse events were itching, tingling, headache, discomfort, and burning sensation. Poreisz et al summarized findings from 567 sessions involving 102 participants to demonstrate that adverse effects were quite minor in severity. For example, mean ratings of itching during stimulation were 1.6 out of 5. Similar ratings were given for tingling (1.74), burning (1.59), headache (1.4), pain (1.41), difficulties in concentrating (1.73), nervousness (1.0), and unpleasant sensation (1.24). The highest rated adverse effect was fatigue (2.17), although the authors note that this factor was likely influenced by the completion of sometimes monotonous tasks while also receiving tDCS.*

*There is a strong evidence that tDCS is extremely safe. A recent review reported that "To date, based on over a total 33,000 sessions and over 1000 subjects who received repeated tDCS sessions, there is no evidence for*

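### The protocol does not say whether active and sham tDCS are compared within or between participants, nor that condition or session order is randomised or counterbalanced

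*Protocol*

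**What the plan says.** Hypotheses 2.1 and 2.2, listed under Aim 1 in Protocol section 1, set active against placebo stimulation in ACLR patients. For corticospinal excitability (CSE), an increase is expected "after one session of active tDCS and no changes in CSE after placebo tDCS". For quadriceps performance: "Patients after ACLR will demonstrate greater RTD/isometric strength after one session of active tDCS and no changes in RTD/isometric strength after placebo tDCS".

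Section 8 (Procedures) says "This study will consist of two collections separated by at least 48 hours", with the full test battery before and after a tDCS session. The tDCS subsection gives active stimulation for the whole bike ride, "while the sham a-tDCS will be applied for only the first 30 seconds". Section 9 adds, for adults, "Participants must complete both sessions to receive the compensation".

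Section 6 plans for 30 uninjured participants, and "30 subjects with a history of ACLR will be recruited for this study". Sections 5 and 8 restrict under-18s to one session without tDCS.

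The Data Analysis subsection lists t-tests on demographics, a limb-by-group ANOVA on the strength, TMS and fNIRS measures, and regressions. The only random assignment in the text at hand is that of participant ID codes (section 12).

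**The concern.** Aim 1 is a causal claim about active against placebo stimulation, so how a participant comes to receive one or the other, and in which session, is part of the design. It is settled when session 1 begins and is not a detail that a protocol normally leaves to the SAP.

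The text permits active first for everyone, sham first for everyone, or whatever order suits the day. If all participants have the same order, condition and session number are the same variable, and no later model can separate them. The protocol describes the study as pilot data for a larger grant application, so a confounded estimate would carry forward into that planning.

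**Working it through.** **1. What design do the passages imply?**

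| Element | Protocol | Stated? |
|---|---|---|
| Active versus placebo contrast | Section 1, Hypotheses 2.1 and 2.2 | Yes |
| Two sessions, each with its own pre- and post-test | Section 8, Procedures | Yes |
| Delivery of active and of sham | Section 8, tDCS | Yes |
| Adults must attend both sessions to be paid | Section 9 | Yes |
| One session active, the other sham, in the same person | none | Inferred only |
| Rule for assigning condition or order | none | No |
| Condition, time or period term | Section 8, Data Analysis | No |

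A two-period crossover is the natural reading of the first four rows. If a parallel comparison was meant, the rule for assigning participants to active or sham is equally absent.

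**2. What does an unbalanced order do to the estimate?**

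Let τ be the true active-minus-sham difference in pre-to-post change. Let π be the session-2-minus-session-1 difference in that change when the condition is the same.

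- Active then sham: expected active-minus-sham difference = τ − π.
- Sham then active: expected difference = τ + π.
- With m of n participants active first, the simple mean has expectation τ + π(n − 2m)/n.

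If m = n this is τ − π, if m = 0 it is τ + π, and if m = n/2 it is τ. A stable shift in level between sessions is not part of π, because it appears in both the pre-test and the post-test of a session and drops out of the change.

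**3. How large could the effect be? (illustration only)**

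The protocol gives no alpha, power, effect size or SD, so there is no figure of its own to reproduce. Inputs:

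- n = 30 is the ACLR target and a ceiling for Aim 1, because under-18s receive no tDCS. n = 20 is an assumed lower value.
- Two-sided alpha of 5% is assumed.
- d = |π| / SD of the paired difference, assumed at 0.2, 0.3 and 0.4.
- τ = 0, with the same order for everyone (the worst case).

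The paired t statistic then follows a non-central t with n − 1 degrees of freedom and non-centrality d√n. The rejection probability is P(|T| > t₀.₉₇₅,ₙ₋₁), with critical value 2.045 at n = 30 and 2.093 at n = 20.

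| d | d√30 | Rejects, n = 30 | d√20 | Rejects, n = 20 |
|---|---|---|---|---|
| 0.2 | 1.095 | 18.5% | 0.894 | 13.6% |
| 0.3 | 1.643 | 35.5% | 1.342 | 24.7% |
| 0.4 | 2.191 | 56.3% | 1.789 | 39.7% |

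**4. Does a balanced order remove it?**

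Take 15 participants per sequence and estimate τ as the average of the two sequence means, with pooled within-sequence variance and 28 degrees of freedom. In 40,000 simulated trials at each of d = 0.1, 0.2, 0.3 and 0.5, the bias was about zero and the false-positive rate was 4.9% to 5.1%.

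**The case against.** The strongest reply is that silence is not a flawed design. A reader might infer that the order is non-random, but nothing in the protocol fixes such an order. It simply does not say. The document is also a summary form, and the consent forms it mentions are not shown and might describe assignment. This stands to the extent that bias is possible, not established. It does not excuse the gap in section 8, which is where assignment belongs.

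A reader might also infer that practice with maximal contractions, familiarity with TMS or left-over soreness would by themselves be mistaken for a tDCS effect. The documents do not support that. Each session has its own pre-test, which removes a stable level shift, and three sub-maximal practice trials precede the maximal contractions. The soreness text in section 10 is weak support: "Subjects may experience mild muscle soreness 24-48 hours after the testing session" meets the minimum gap only at its 48-hour edge. What survives is narrower: an order effect on the within-session change, such as a larger practice gain in one session or more fatigue in the other.

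Finally, the period effects of 0.2 to 0.4 SD have no source in the protocol, and a common order for everyone is the extreme case. Both points are correct, so the rejection rates are not predictions for this trial.

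**Conclusion.** The point holds in this limited form. The protocol sets up an active-versus-placebo comparison over two sessions but does not state whether it is within or between participants, gives no rule for assigning condition or order, and lists no analysis term for condition, time or period. A fixed or convenience order would comply with it, and under a common order a session difference in pre-to-post change could not be separated from a tDCS effect afterwards.

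The sizes in the table are conditional on assumed period effects, a two-sided 5% test, no true effect and one order for all. With fewer than 30 adults stimulated they are lower, but still well above 5% at n = 20. The conclusion that the design and assignment must be stated does not depend on them, and it holds equally if a parallel design was intended. The change should be made before the first stimulated session, because analysis cannot repair a common order.

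**What to change.** State in section 8 that Aim 1 is a two-period crossover. Every participant who receives tDCS is randomised 1:1 to active-then-sham or sham-then-active, from a list generated in advance and concealed until session 1. This should cover the ACLR adults, and the uninjured controls if they are stimulated. The protocol should say whether they are, because section 10 speaks of monitoring discomfort around tDCS in age-matched controls as well as patients.

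In Data Analysis, define the Aim 1 estimate as the active-minus-sham difference in pre-to-post change, adjusted for period. If a parallel design was meant, say so and randomise participants to active or sham in the same way.

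The cost is a computer-generated list, a few sentences of protocol text and about one degree of freedom (28 instead of 29 at n = 30). Sample size, visits and stimulation settings stay as they are.

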**Demographic Data**

*Each participant will be asked to self-report their leg and hand dominance, describe sport participation, date of birth, age, height, weight, and sex.*

**Central Nervous System testing**

*Cortical excitability (via TMS) and cortical activation (via fNIRS) will be evaluated during 2 different tasks: 1) While seated in a dynamometer (strength testing device) and activating their quadriceps muscle at 5% of their maximal torque, and 2) during a single limb stance position. Participants will be secured into a harness system during the single limb stance task to prevent loss of balance. See next 2 sections for specific TMS and fNIRS procedures. Participants < 18 years old will not undergo TMS testing. A separate consent form has been created for participants < 18 years excluding the TMS procedure.*

**TMS testing**

*TMS will be delivered using a MagStim 200 Stimulator with a double circular coil (Magstim Ltd, Wales, UK). All TMS testing procedures will be performed for both hemispheres and during both of the tasks mentioned above. Electrical activity from multiple lower extremity muscles will be collected using surface EMG electrodes placed on the skin. One or more of the following muscle groups will be collected: quadriceps, hamstrings, triceps surae. Subjects will wear a closely fitting cap. First, the site on the scalp where a TMS pulse of ~50% maximum stimulator output produces the greatest muscle response (hotspot) will be identified. The active motor threshold*

(AMT) will be determined by finding the amount of stimulator output needed to generate at least 5/10 motor evoked potentials that exceed 100  $\mu$ V. Patients will be activating the target muscle at 5% their MVIC during each pulse by receiving visual feedback of their force. After determining the AMT, 10 pulses at intensities between 80% AMT and 140% AMT (at 10% intervals) will be delivered.

Each time the stimulus intensity is changed, a test stimulus will be triggered away from the participant to ensure the correct intensity and that no noise is present in the EMG signal.

**Strength testing**

Testing will take place in the Exercise Testing Lab (Room 109, Health Sciences Building). Strength testing will consist of maximal voluntary contractions of the quadriceps muscles of both legs. This testing is performed routinely during physical therapy for individuals with knee pathology. Participants will be seated upright in a dynamometer (HUMAC NORM), a device that secures their pelvis and limbs and resists the patient's attempt to straighten the knee from 90 degrees of knee flexion. The participant will be asked to kick as hard as they can against the arm of the dynamometer to calculate their maximum volitional isometric contraction (MVIC). The amount of force/torque produced will then be recorded. Prior to the MVICs, a series of three sub-maximal practice trials will be performed to familiarize each participant with the task. Three MVICs will then be performed and recorded for analysis. Two additional (one warm up and one test set) sets of five repetitions will be performed to test both quadriceps and hamstring strength through the patients full available range of motion.

**Questionnaires**

Multiple questionnaires will be administered to examine pain, knee function, emotions and fear of reinjury, and activity level. See appendix B.

**Transcranial direct current stimulation (tDCS)**

a-tDCS (Soterix 1x1, Soterix Medical Inc, NY, NY) will be delivered over the primary motor cortex contralateral to the surgical limb (i.e. hot spot for the vastus medialis muscle representation found during TMS testing). A pair of carbon electrodes placed in saline-soaked sponges (surface area: 5 x 7  $\text{cm}^2$ ) will be secured to the scalp using straps (Soterix EASYstrap). The anode will be centered over the hotspot while the cathode will be placed on the right supraorbital area. a-tDCS will be administered while the participant rides a stationary bike for 20 minutes. The bike seat will be adjusted for each participant so that maximal knee flexion range of motion will be 90 degrees. Participants will also be instructed to maintain a neutral ankle angle. Verbal feedback provided by an investigator will be provided throughout the intervention to maintain the neutral ankle position. The standardized seat position and ankle position is to prevent the participant from using their ankle plantarflexors during the pedaling motion. Stationary bike riding was chosen as this task is commonly performed early after ACLR with minimal stress to the healing graft and requires quadriceps activity. The first 5 minutes will serve as a warmup with the patient maintaining a rate of perceived exertion (RPE) of light or 1 out of 10. Over the next 10 minutes, the resistance will be increased to maintain a RPE of moderate or 3/10. The last 5 minutes will serve as a cool down at the same intensity/resistance as the warm up. Active a-tDCS will be applied at an intensity of 2mA with a 30-second ramp-up and 30-second ramp-down for the entire duration of bike riding, while the sham a-tDCS will be applied for only the first 30 seconds.

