**Anticipated date of Submission:**

**b) Is this a collaboration with another institution (if yes, please move to section 3 c)?**

- Yes
- No

**c) Is each institution doing their own review or will one institution serve as the primary IRB through an Authorization Agreement?**

- Each institution will complete their own review.
- An Authorization Agreement will be signed.

**4. Study Population - Are the human subjects involved in the proposed activity included in the following categories? (check all that apply, at least one box must be checked)**

*Yes. Human subjects are included in this study.*

 Minors	 Pregnant women, human fetuses, neonates
 Prisoners	 AIDS/HIV-positive subjects
 Terminally ill subjects	 Subjects with intellectual disabilities
 Economically and/or educationally disadvantaged persons	 Minorities
 None of the above	 Other Click here to enter text.

**5. Inclusion and Exclusion Criteria - Describe the criteria that define who will be included or excluded in your study sample. If you are conducting data analysis only describe what is included in the data set you propose to use.**

*ACLR Group: Individuals between the ages of 13 and 55 years with a history of ACLR (4 months to 5 years) will be recruited.*

*Uninjured Group: Individuals between the ages of 13 and 55 years without a history of major knee injury or surgery will be recruited for the uninjured group. These participants will be matched to participants in the ACLR group by sex, age, and activity level.*

*Both groups must participate (or participated in prior to surgery) in sports involving jumping, pivoting, cutting on a regular basis to be included. Individuals < 18 years of age will only complete strength testing and questionnaires at one testing session. They will not participate in TMS testing or the intervention (tDCS with stationary bike riding).*

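### The cathode is fixed on the right while the anode follows the operated knee, so left- and right-knee patients would receive two tDCS montages that are not mirror images

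*Protocol*

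**What the plan says.** Protocol Section 8, under Transcranial direct current stimulation (tDCS), gives two placement rules. Stimulation "will be delivered over the primary motor cortex contralateral to the surgical limb", at the vastus medialis hotspot found by TMS. For the electrodes themselves, "The anode will be centered over the hotspot while the cathode will be placed on the right supraorbital area". The first rule depends on which knee was operated on; the second does not.

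Section 5 sets no condition on the operated side: "Individuals between the ages of 13 and 55 years with a history of ACLR (4 months to 5 years) will be recruited". Of participants under 18 it says "They will not participate in TMS testing or the intervention". Under TMS testing in Section 8, "All TMS testing procedures will be performed for both hemispheres", so a hotspot is available on either side. Section 6 states that "30 subjects with a history of ACLR will be recruited for this study". Section 8 also says "This study will consist of two collections separated by at least 48 hours".

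Aim 1 in Section 1 concerns the effect of one tDCS session on corticospinal excitability and quadriceps performance. The same section says the results will serve as pilot data for a larger grant application on multiple sessions.

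**The concern.** The montage is the intervention, and the two rules together do not define a single one. The current path between the electrodes would depend on surgical side: across the midline for right knees, within one side of the head for left knees. An average over all treated patients would describe neither montage, and the weights would depend on who happens to enrol.

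The section is otherwise careful about uniform delivery. It fixes the current, the duration and the exertion levels, and gives a reason for fixing posture on the bike: "The standardized seat position and ankle position is to prevent the participant from using their ankle plantarflexors". It gives no reason for a cathode that stays on the right.

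What is at stake is the interpretation of the Aim 1 estimate and its use in planning the larger study. Anyone designing that study or repeating this one needs to know which montage the estimate refers to.

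**Working it through.** **Step 1. Apply both rules to each operated side.**

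| Operated knee | Anode (opposite the knee) | Cathode (always right) | Relation |
|---|---|---|---|
| Right | Left motor cortex | Right supraorbital | Opposite sides |
| Left | Right motor cortex | Right supraorbital | Same side |

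The mirror image of the right-knee montage is a right motor cortex anode with a left supraorbital cathode. The text never assigns that placement.

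**Step 2. Look for text that resolves it.** Section 5 does not limit the operated side. Nothing else in the protocol ties the cathode to the knee or the anode, or explains a fixed right position. Mapping both hemispheres makes either anode side workable. It is only weak evidence that both are expected, since the limb comparison planned under Data Analysis could also explain it. The main support is the absence of any side restriction.

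**Step 3. What the average describes.** Let E_cross and E_same be the mean effects of the opposite-side and same-side montages, D = E_same − E_cross (either sign, possibly zero), and p the share of left knees among treated patients. The protocol gives neither D nor p.

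- Average = (1 − p)·E_cross + p·E_same
- Average − E_cross = pD
- Average − E_same = −(1 − p)D

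With p = 1/2 (assumed), the average lies 0.50D from each montage's own effect. With p = 1/3 (assumed), it lies 0.33D from the opposite-side effect and 0.67D from the same-side effect.

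**Step 4. Could the pilot estimate D afterwards?** Section 6 gives 30 ACLR participants. This is a maximum for treatment, because any under 18 receive no tDCS. Assume that each treated patient has one active and one sham session, and that the SD of the within-person active-sham difference is the same for both montages. In units of that SD:

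95% half-width for D = t(0.975, n1 + n2 − 2) × √(1/n1 + 1/n2)

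| Assumed split | Calculation | Half-width |
|---|---|---|
| 15 v 15 | 2.048 × √(2/15) | 0.75 |
| 20 v 10 | 2.048 × √(3/20) | 0.79 |
| 10 v 10 (20 adults) | 2.101 × √(1/5) | 0.94 |

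The splits and the 20-adult case are assumptions. Even a precise left-right comparison would not isolate montage, because left-knee patients also differ in which hemisphere is stimulated.

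**The case against.** The strongest objection is that no harm is shown. Nothing in the protocol says the two montages act differently on motor threshold, recruitment slope, strength or rate of torque development. This stands: the size and sign of D are unknown, and no dilution of the effect can be claimed.

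Second, montage is constant within a person, so a within-person active-sham contrast is not biased. This also stands, with one caution. The two sessions, together with hypotheses about active and placebo stimulation, make a crossover plausible, but no sentence says each patient receives both. The reassurance and the half-widths both rest on that reading.

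Third, the half-widths concern a left-right comparison that no aim or analysis asks for. That is true. They do not measure harm from the wording; they show only that the ambiguity could not be cleared up from the pilot's own data.

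Fourth, the word for the right side may be a slip for contralateral, and one investigator collects all the data, so delivery may be correct in practice. This is possible, but it does not repair the document. Staff who follow the sentence would place a left-knee patient's cathode on the anode side. If they silently correct it, the protocol misdescribes what was delivered.

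Fifth, mirrored montages still differ in the hemisphere stimulated. That is so, but it follows from targeting the operated limb, whereas the cathode asymmetry is avoidable.

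A related gap is that Section 10 mentions tDCS in controls as well as patients. If controls are stimulated, they have no operated limb and the anode rule gives them no side.

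**Conclusion.** The concern holds. As written, the placement rules assign two non-mirror montages according to operated side, and nothing in the protocol reconciles them. This follows directly from the text and needs no assumption beyond both left and right knees being enrolled, which the criteria allow.

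The consequence is limited to what the Aim 1 average means. It would sit pD from one montage's effect and (1 − p)D from the other's, with D unknown and possibly zero. No bias in the active-sham contrast is claimed, provided each patient receives both conditions. The case for acting is that this is an operative delivery instruction, the pilot is meant to inform a larger study, the question could not be settled afterwards, and the correction is almost free. It should be corrected, but it does not invalidate Aim 1.

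**What to change.** In the electrode sentence, replace the fixed cathode position with: *the supraorbital area contralateral to the anode (ipsilateral to the surgical limb)*. Right-knee placement stays as it is, and left-knee patients receive its mirror image. If controls are stimulated, the main phrase still works once their anode side is defined; the parenthesis applies only to ACLR patients.

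If a fixed right cathode is deliberate, say so in the same sentence.

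The cost is one phrase in the delivery instruction. It needs no extra participants, equipment, sessions, recorded variables or analyses. The difference in stimulated hemisphere between left- and right-knee patients remains.
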